- h. All events of possible drug-induced liver injury with **hyperbilirubinaemia** defined as **ALT \geq 3xULN** (without elevated CPK, and/or myoglobin) **and bilirubin \geq 2xULN ($>35\%$ direct)**

- i. All events of possible liver injury with **increased INR** defined as **ALT \geq 3xULN** (without elevated CPK, and/or myoglobin) **and INR >1.5** . If INR measured termed 'Hy's Law' events (INR measurement is not required and the threshold value stated will not apply to patients receiving anticoagulants).

NOTE: bilirubin fractionation is performed if testing is available. If testing is unavailable, record presence of detectable urinary bilirubin on dipstick indicating direct bilirubin elevations and suggesting liver injury. If testing is unavailable and a subject meets the criterion of total bilirubin \geq 2xULN, then the event is still reported as an SAE. If INR is obtained, include values on the SAE form. INR elevations >1.5 suggest severe liver injury. (See Appendix C).

NOTE:

ULN (Upper Limit of Normal) as determined by the reference range of the local lab

All liver toxicities must be reported to the Sponsor (Northwell Health) and GSK.

Subjects that meet liver stopping criteria (See Appendix C) MUST be reported to GSK within 24 hours.

In the case of a LIVER STOPPING EVENT, follow up assessments should be completed (see Appendix C).

Laboratory and Other Safety Assessment Abnormalities Reported as AEs and SAEs: Any abnormal laboratory test results (hematology, clinical chemistry, or urinalysis) or other safety assessments (e.g., ECGs, radiological scans, vital signs measurements), including those that worsen from baseline, and felt to be clinically significant in the medical and scientific judgment of the investigator are to be recorded as AEs or SAEs.

NOTE: However, any clinically significant safety assessments that are associated with the underlying disease, unless judged by the investigator to be more severe than expected for the subject's condition, are **not** to be reported as AEs or SAEs.

Adverse Events of Special Interest: The following AEs should be monitored closely and reported to the study sponsor immediately.

1. **Serious hypersensitivity reaction or Infusion Reactions** (See Section: Study Drug Administration and Considerations)
2. **Suicidality:** Some autoimmune diseases have an increased risk of suicidal behavior and/or ideation [Bachen, 2009; Timonen, 2003; Stenager, 1992]. For this reason in studies of patients with autoimmune disease, patients should be clinically assessed for suicidal ideation and/or behavior at each visit. If destructive tendencies are suspected, the subject should be referred to a psychologist or other appropriate specialist for evaluation.
3. **Malignancy**
4. **Serious infections**, including herpes zoster and opportunistic infections
5. **Progressive multifocal leukoencephalopathy (PML)**. PML resulting in neurological deficits, including fatal cases has been reported in SLE patients receiving immunosuppressant pharmacotherapy, including belimumab. A diagnosis of PML should be considered in any subject presenting with new-onset or deteriorating neurological signs and symptoms. The subject should be referred to a neurologist or other appropriate specialist for evaluation. If PML is confirmed, study agent should be discontinued and consideration should be given to stopping immunosuppressant therapy. **If PML is suspected, this should be immediately reported to the Medical Monitor.** The appropriateness of continuing study agent, while the case is being assessed, should be discussed.
6. **Abnormal liver enzymes** (See Appendix C). While previous studies of belimumab in lupus have shown no causal relationship between the drug and liver toxicity, liver function will be monitored in all subjects throughout the study (See Appendix C).

Pregnancy:

Any pregnancy that occurs during study participation must be reported using clinical trial pregnancy form. To ensure subject safety, each pregnancy must be reported within 2 weeks of learning of its occurrence to the lead site and sponsor. The pregnancy must be followed up to

determine outcome (including premature termination) and status of mother and child. Pregnancy complications and elective terminations for medical reasons must be reported as an AE or SAE. Spontaneous abortions must be reported as an SAE. Pregnancy testing will occur at every study visits and at 16 weeks after the last treatment dose.

NOTE: Any SAE occurring in association with a pregnancy brought to the investigator's attention after the subject has completed the study and considered by the investigator as possibly related to the study treatment, must be promptly reported to the lead site as well as GSK.

Adverse Event and Serious Adverse Event Reporting:

The investigator or site staffs are responsible for detecting, documenting and reporting events that meet the definition of an AE or SAE.

- All AEs must be reported to the coordinating site.
- All SAEs must be reported to the coordinating site and local IRB within 24 hours. The coordinating site will report all SAEs to the coordinating site's IRB, the sponsor and the FDA.

All AEs and SAEs must be reported on an Adverse Event/Serious Adverse Event case report form. The study investigator is responsible for noting the relationship of the event to the study drug, the severity of the drug (criteria for grading toxicity will be based on NCI's Common Terminology Criteria for Adverse Events version 4.03), the actions taken with the investigational product, and any other medications used to treat the adverse event or serious adverse event.

Time Period and Frequency of Detecting AEs and SAEs:

The investigator or site staffs are responsible for detecting, documenting and reporting events that meet the definition of an AE or SAE. AEs will be collected from the start of the study treatment until the end of the study. SAEs will be collected from the start of the study treatment until the end of the study. All SAEs will be reported to the coordinating site, sponsor and IRB within 24 hours.

NOTE: Any SAEs assessed as **related** to study participation (e.g. study treatment, protocol-mandated procedures, invasive tests, or change in existing therapy) or related to a GSK concomitant medication, will be recorded from the time a subject consents to participate in the study up to and including any follow up contact.

Study Procedures & Assessments:

The following assessments will occur throughout the study (see Appendix A for schedule of events):

- Informed Consent and Inclusion/Exclusion Criteria will be assessed at the screening visit. After a subject signs the informed consent they will enter the screening period (≤ 2 weeks) and have eligibility determined prior to Day 0.

Laboratory assessments:

- a. CBC, Comprehensive metabolic, GGT, ESR, CRP, CPK, serum myoglobin, immunoglobulins, urinalysis and urine pregnancy test will be collected at screening.
- b. CBC, Comprehensive metabolic, GGT, ESR, CRP, CPK, serum myoglobin, immunoglobulins and urinalysis **collected within 2 weeks prior to screening can be used** for eligibility determination.

- c. Testing for latent TB is a standard of care for patients on immunosuppressive therapy and results will be obtained **from their medical record**. If no TB history is found for these patients, a Quantiferon Gold or PPD test will be performed prior to Day 0 as part of **standard of care**.
- d. Hepatitis status will be obtained from patients' **medical records**. If unavailable, testing will be done as part of **standard of care** during the screening period.
- Vital signs will be assessed prior to infusion and after the infusion at every visit.
- Adverse events assessed at every visit. Criteria for grading toxicity will be based on NCI's Common Terminology Criteria for Adverse Events version 4.03. (Adverse Events/Serious Adverse Events (CTCAE Version 4.03)
- A Physical Exam will be performed by the Investigator at Screening, Day 0, Week 8, 16, 24, 32, 40, 52, & 64.
- Urine Pregnancy testing for WOCBP will be conducted at each study visit and 16 weeks after last dose. Urine pregnancy tests must be completed < 7 days prior to the first dose and prior to each IP administration, but not more than once a month. In the event that the urine pregnancy test is indeterminate, a serum pregnancy test will be done.
- Laboratory tests: CBC, Comprehensive metabolic, GGT, ESR, CRP, CPK, myoglobin and urinalysis will be collected at every study visit and follow up week 64.
- An immunoglobulin panel will be collected and assessed at: Screening, Week 40, & 64. Under special circumstances monthly IgG monitoring may be required (see Section: Study Design, part f) and will be performed as part of standard of care.
- Flow Cytometry and RNA-seq are collected at: Day 0, Week 8, 40, Week 48, & Week 60 or 64.
- Cytokine levels (and optional research Northwell only) will be measured at: Day 0, Week 40, & Week 60 or Week 64.
- Patients should be clinically assessed for suicidal ideation and/or behaviour at each study visit using the Columbia Suicide Severity Scale (C-SSRS)
- The Investigator will complete a Physician Global Assessment (PGA, a VAS scale of 10cm), Manual Muscle Test-8 (MMT-8), & Myositis Disease Activity Assessment Tool (MDAAT) at Screening, Day 0, Week 8, 16, 24, 32, 40, 52, & 64
- The Investigator will complete a Muscle Damage Index (MDI) assessment at Screening, Week 40 and Week 64
- Health Assessment Questionnaire (HAQ) and Patient Global Assessment (PGA, a VAS scale of 10cm) will be completed by subjects at Screening, Day 0, Week 8, 16, 24, 32, 40, 52, & 64
- Post study follow up phone call with subject conducted at Week 72 and 84.
- Patients who previously received IVIG and with Hep B core IgG positive and Hep B sAB positive will undergo surveillance with Liver function test, Hepatitis Panel and Viral Load every 3 months.

Data Safety Monitoring Plan:

The principal investigator and two independent physicians, designated by the Principal Investigator, will be responsible for the oversight of the data safety monitoring plan. The committee will meet every 6 months to evaluate the rate of unanticipated adverse events. If any

safety signals are identified, recommendations to changes in the protocol or consent will be defined by the committee. Benefit-to-risk assessment will be made in order to determine if the study should continue. The results of these regular meetings will be recorded and disseminated to all participating clinical sites.

Feinstein Biostatistics Unit BUDDY System: Data Management

The Biostatistics Unit (BU), within The Feinstein Institute for Medical Research (FIMR), provides state-of-the-art statistical and data management support to the research investigators at Northwell Health as well as other medical research institutions in the New York area. Its staff of ten PhD and Masters level statisticians and two senior applications programmers has extensive experience in the design, data management, and analysis of hundreds of clinical research projects, including over 250 clinical trials. Primary expertise is in clinical trials, diagnostic testing and screening, the development of predictive models for prognosis, and development of protocols and grant applications.

The Biostatistics Unit provides data management support through its “BUDDY” system (“Biostatistics Unit Database Designed for You”). BUDDY is a highly customized, secure, HIPAA-compliant, web-based database application. It is particularly suited to studies with longitudinal and relational data structures, especially clinical trials. The cost of database development may vary depending upon features requested by the user, including, but not limited to: case report form development, number of unique data screens, transfer of data between another system and BUDDY, data validation checks between screens, image file storage, special queries or reports, translation of adverse event descriptions into MedDRA, and data submission tracking.

The Biostatistics Randomization Management System (BRMS) is a secure, HIPAA-compliant, web-based application that allows investigators to randomize subjects into randomized clinical trials (RCTs) using their personal computer. The BRMS allows for multi-center, stratified, and single/double blinded RCTs, using permuted blocks. Randomization notifications are automatically sent to the PI and other authorized personnel. Using BRMS is a good way to maintain compliance in RCTs.

Statistical Considerations

SPECIFIC STATISTICAL AIMS

The primary objective of the study is to compare subjects in the Belimumab group and subjects in the placebo group with respect to response (improvement) at week 40.

The specific aims of the study are to compare the two treatment arms (Belimumab vs. Placebo [P vs. B]), during the 40-week randomized phase of the study, with respect to the following:

1. Response at week 40.
2. Flare rates during the 40-week treatment period.
3. Time-to-achieve (initial) improvement during the 40-week randomized phase of the study
4. Duration of improvement during the 40-week randomized phase of the study, among those who achieved improvement (this is essentially a time-to-flare/relapse analysis from the time that you achieved improvement)
5. Change in muscle enzyme levels (CPK, myoglobin) from baseline to week 40
6. Change in MMT-8 from baseline to week 40
7. Change in prednisone dose from baseline to week 40

8. Proportion of subjects able to reduce prednisone dose to ≤ 5 mg at week 40
9. Change in B cell populations, immunoglobulin levels and BLys levels from baseline to week 40.
10. Change in autoantibody titers from baseline to week 40.
11. Rates of SAEs and AEs experienced

STATISTICAL METHODS

All subjects will be analyzed according to the intention-to-treat [ITT] principle. A subject will be considered evaluable and will be included in the intention-to-treat analysis if he/she received at least the first five of the planned infusions during the randomized phase of the study. Subjects who do not get the first five infusions will be considered ‘drop-outs’. It should be noted that the study protocol calls for patients remaining on their treatment assignment. However, adjustments in dosages of medications used in their ‘standard care’ are permitted during the first 8 weeks. Analyses that take into account the actual treatment received (e.g. accounting for compliance, etc.) will be carried out as a secondary analysis (per protocol [PP] analysis).

1. For specific aim 1, the two treatment arms [B vs. P] will be compared with respect to the proportion of subjects who respond to treatment at 40 weeks (improvement according to definition), using either a chi-square test or Fisher’s exact test, as appropriate.
2. For specific aim 2, either a chi-square test or Fisher’s exact test, as appropriate, will be conducted to compare the proportion of subjects who had any flares during the 40-week randomized phase. For this analysis, each subject will be categorized at the end of 40 weeks as having had one or more flares or not having had any flares. In addition, we can also examine the total number of days that a subject had a specific flare during the course of the 40-week treatment, and compare the two treatment arms using the ‘Incidence density ratio’ method.
3. For specific aim 3, standard methods for survival analysis will be carried out. The Kaplan-Meier (KM) product limit method will be used to estimate overall “time-to-achieve (initial) response/improvement”. Ninety-five percent confidence intervals will be calculated using Greenwood’s formula for computing the standard error. Subjects who have not achieved improvement as of week 40 will be considered ‘censored’ for the event (event=improvement/response).
4. For specific aim 4, similar methods as indicated for specific aim 3 will be conducted. The analysis for this aim will be limited to the subset of subjects in each treatment arm who show improvement at anytime during the randomized phase of the trial. A subject who has not flared/worsened/relapsed as of week 40 will be considered ‘censored’ for the event (event=flare/relapse).
5. For specific aims 5, 6, 7, 9 and 10, each of the outcome variables of interest (uncensored continuous or categorical) will be analyzed separately, using a mixed model approach to repeated measures analysis of variance (MMRMANOVA) with the main effects of treatment arm (B vs. P), Disease type (PM vs DM), Disease Severity (Severe vs. Less Severe) and time (baseline vs. 40 weeks). If feasible, statistical interactions between

treatment and time (baseline vs. week 40; or all available data at each study visit) or other factors of interest will be examined (e.g. Treatment X Disease Type; Treatment X Disease Severity). The treatment-by-time interaction term, will demonstrate whether the trajectories (or patterns of change) in the outcomes of interest are different between treatment groups. Data transformations may be used, in order to meet the necessary assumptions for the mixed models analyses. If transformations do not achieve the assumptions needed, a rank transformation or an appropriate non-parametric method will be considered.

If the analysis using a mixed model approach is not feasible due to the pattern of the data, then, a simplified analysis comparing the two treatment arms with respect to percent change (reductions) in muscle enzymes, MMT-8 and prednisone dose will be carried out using either a t-test or the Mann-Whitney test, as appropriate. A chi-square test or Fisher's exact test, as appropriate, may also be used if the continuous measures are grouped according to pre-specified categories (e.g. reduction in CPK will be categorized as No Response, Partial Response or Complete Response according to whether the percent reduction was <20% vs. 20%-70% vs. >70%, respectively).

6. For specific aim 8, the proportion of subjects who were able to reduce their daily prednisone dose to ≤ 5 mg at week 40, will be compared using either a chi-square test or Fisher's exact test, as appropriate.
7. For specific aim 11, either a chi-square test or Fisher's exact test, as appropriate, will be conducted to compare the proportion of subjects who experienced any SAEs or AEs during the randomized phase of the study. For this analysis, each subject will be categorized at the end of 40 weeks as having had any SAEs/AEs or not having any SAEs/AEs.

Multivariable analyses (logistic, cox) will be conducted for the above outcomes, if feasible. However, this may be limited by the sample size.

SAFETY DATA

There will be no formal interim analyses or formal statistical stopping rules. However, statistical summaries of adverse event rates using 95% exact confidence intervals will be provided to the data safety monitoring board as need. During regular bi-annual meetings the data safety monitoring board will evaluate the overall rate of adverse events and unanticipated problems. Upon review the group will determine whether there are any changes needed to the anticipated benefit-to-risk assessment and if the study should continue. The results of these regular meetings will be recorded and disseminated to the other participating clinical sites. Safety data will be collected in the form of adverse events (AEs), serious AEs (SAEs) and laboratory parameters (e.g., hematology, chemistry, etc.). AEs will be recorded with the date of onset, severity, relationship to study drug, and disposition. AEs will be translated into a standard classification system such as COSTART or MedDRA. AE data will be summarized according to incidence rates, by treatment arm and by whether or not the AE was treatment related. AEs will be summarized using descriptive statistics and tabulated according to treatment group for each strata. The AE report will be descriptive, rather than inferential.

SAMPLE SIZE CONSIDERATIONS

We plan to enroll 30 evaluable patients with 15 in each of two treatment arms [B vs. P].

From available trials in IIM, there is an observed placebo effect of 0%-40% at 12 weeks^{9,10} and 0% at 52 weeks⁹. These results demonstrate that the placebo response rate at 40 weeks can be very variable. One clinical study looking at rituximab in myositis was the first prospective, double-blind, randomized trial in myositis and the largest clinical trial ever performed in the inflammatory myopathies¹⁶. This trial employed a unique design; subjects were divided into two groups: early-start and delayed-start of rituximab. Overall, 83% of enrolled subjects (with severe refractory disease) met the DOI by the end of the trial, despite lack of statistical significance between groups. An alternate double-blind, placebo-controlled trial of etanercept (50 mg subcutaneously weekly for 52 weeks) where 16 subjects were randomized showed that: all 5 subjects receiving placebo were treatment failures (median time to treatment failure: 148 days)¹⁷. In contrast, 5 of 11 subjects in the etanercept arm were successfully weaned off prednisone; the median time to treatment failure in this group was 358 days ($p = 0.0002$). This data shows that for myositis trials, placebo response is often close to 0%. In order to achieve a clinically meaningful difference between study treatment arms, the response rate of the treatment group would need to be at least 50%.

We hypothesize (optimistically) the response rate at 40 weeks in the placebo arm to be 5%. We further assume that a magnitude of difference of 45% would be clinically meaningful (this corresponds to a 50% response rate in the Belimumab arm).

Based on the assumption that a difference of 45% in response rates at 40 weeks between Placebo and the investigational agent, Belimumab, would be clinically meaningful, then, a two group chi-square test ($\alpha=0.05$, two sided test) will yield 80% power to detect a difference between the Placebo arm week 40 response rate of 5% and a Belimumab-treated arm week 40 response rate of 50% (Odds ratio=19) when the sample size in each group is 15, assuming the dropout rate is 0%.

Table 1 below shows the sample size requirements for various pairs of (hypothesized) 40-week response rates and assumptions on what would be a clinically meaningful difference between treatment arms. Corresponding sample sizes are provided for the specified range of parameters. Calculations were based on a two-sided chi-square test to achieve 80% power ($\alpha=0.05$).

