Screening: Once the patient signs the consent form, a screening period of up to two weeks will initiate to determine the patient's eligibility for the study, prior to entering the randomization phase. Only eligible patients will enter the randomization phase.

Randomized Phase: Monthly infusions (of either B or P) will start at week 0 and continue every four weeks until week 36 (10 months) for the “randomized” phase of the study. In addition, there will be a “loading dose” at week 2 (per drug [IND] specifications). The loading dose will consist of either Belimumab or Placebo (saline) in the B or P treatment arms, respectively.

Open Label Phase: Monthly infusions (of B) will start at week 40 and continue every four weeks until week 64 (6 months) for the “open-label” phase of the study.

A comprehensive evaluation of the patient (Physical exam and history, vital signs, AEs, CBC and metabolic panel, GGT, myoglobin, pregnancy test, urinalysis, ESR, CRP, CPK, immunoglobulins, muscle and health evaluations, physician global assessment, patient self-assessments, serum level sampling) will be conducted at weeks 0, 8, 16, 24, 32, 39-40, 52, 64. A less comprehensive set of evaluations (vital signs, AEs, CBC and metabolic panel, GGT, pregnancy test) will be conducted at weeks 2, 4, 12, 20, 28, 36, 40, 44, 48, 56, 60. A detailed schedule of visits and procedures is outlined in appendix A.

A telephone follow-up conversation will also be conducted at weeks 72 and 84.

Optional Exploratory Studies

Blood based biomarker assessments and blood based RNA assessments will be performed on stored samples for consenting patients at Northwell Health only. See Appendix A (schedule of events).

b. Randomization:

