Appendix C.: Liver Chemistry Stopping and Follow Up Criteria

Liver chemistry stopping criteria

Liver chemistry stopping and increased monitoring criteria have been designed to assure subject safety and evaluate liver event etiology (in alignment with the FDA premarketing clinical liver safety guidance). These criteria have been amended for this myositis protocol to accommodate for a specific population of myositis patients with ALT/AST abnormalities as a result of muscle injury. Baseline bilirubin, GGT and INR must be at or near normal. (Note: ULN – upper limit of normal as determined by the reference range of the local lab. All liver toxicities must be reported to the Sponsor (Northwell Health). Subjects that meet liver stopping criteria MUST be reported to GSK within 24 hours.)

- ALT Absolute:
 - ALT \geq 8xULN (without elevated CPK, and/or myoglobin)
 - If ALT \geq 8xULN **and serum GGT \geq 3xULN** (irrespective of CPK and/or myoglobin values)
- ALT Increase:
 - ALT \geq 5xULN but $<$ 8xULN (without elevated CPK, and/or myoglobin) **and GGT \geq 3xULN**, persists for \geq 2 weeks
 - ALT \geq 3xULN but $<$ 5xULN (without elevated CPK, and/or myoglobin) **and GGT \geq 3xULN**, persists for \geq 4 weeks
- Bilirubin: ALT \geq 3xULN and bilirubin \geq 2xULN ($>$ 35% direct bilirubin) ^{a, b}
- INR: ALT \geq 3xULN and INR $>$ 1.5, if INR measured ^b
- Cannot Monitor:
 - ALT \geq 5xULN but $<$ 8xULN (without elevated CPK, and/or myoglobin) **and GGT \geq 3xULN** and labs cannot be monitored weekly for \geq 2 weeks
 - ALT \geq 3xULN but $<$ 5xULN (without elevated CPK, and/or myoglobin) **and GGT \geq 3xULN** and labs cannot be monitored weekly for \geq 4 weeks
- Symptomatic: ALT \geq 3xULN (without elevated CPK, and/or myoglobin) **and GGT \geq 3xULN** associated with symptoms (new or worsening) believed to be related to liver injury or hypersensitivity ^c
 - a) Serum bilirubin fractionation should be performed if testing is available. If serum bilirubin fractionation is not immediately available, discontinue study treatment for that subject if bilirubin \geq 2xULN. Additionally, if serum bilirubin fractionation testing is unavailable, **record presence of detectable urinary bilirubin on dipstick**, indicating direct bilirubin elevations and suggesting liver injury.
 - b) All events of ALT \geq 3xULN (without elevated CPK, and/or myoglobin) **and GGT \geq 3xULN**

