- Liver imaging (ultrasound, magnetic resonance, or computerised tomography) and /or liver biopsy to evaluate liver disease: complete Liver Imaging and/or Liver Biopsy CRF forms.

Increased monitoring criteria with continued therapy

Criteria

- For subjects who have had IVIG in the past, additional HBVDNA testing must be completed when ALT or AST elevations increase to $>2.5\times\text{ULN}$ during the study
- If ALT $\geq 5\times\text{ULN}$ and $<8\times\text{ULN}$ (without elevated CPK, and/or myoglobin) and bilirubin $<2\times\text{ULN}$ without symptoms believed to be related to liver injury or hypersensitivity, and who can be monitored weekly for 2 weeks **OR**
- ALT $\geq 3\times\text{ULN}$ and $<5\times\text{ULN}$ (without elevated CPK, and/or myoglobin) and bilirubin $<2\times\text{ULN}$ without symptoms believed to be related to liver injury or hypersensitivity, and who can be monitored weekly for 4 weeks
- If ALT $\geq 5\times\text{ULN}$ and $<8\times\text{ULN}$ (without elevated CPK, and/or myoglobin) and **GGT is $\geq 1.5\times\text{ULN}$** to $< 3\times\text{ULN}$ without symptoms believed to be related to liver injury or hypersensitivity, and who can be monitored weekly for 2 weeks **OR**
- ALT $\geq 3\times\text{ULN}$ and $<5\times\text{ULN}$ (without elevated CPK, and/or myoglobin) and **GGT is $\geq 1.5\times\text{ULN}$** to $< 3\times\text{ULN}$ without symptoms believed to be related to liver injury or hypersensitivity, and who can be monitored weekly for 4 weeks

Required Actions

- Notify the Sponsor (Northwell Health) and GSK within 24 hours of learning of the abnormality to discuss subject safety.
- Subject can continue study treatment
- Subject must return weekly for repeat liver chemistries (ALT, AST, GGT, alkaline phosphatase, bilirubin) until they resolve, stabilize or return to within baseline
- If at any time subject meets the liver chemistry stopping criteria, proceed as described above for Required Actions and Follow up Assessments following ANY Liver Stopping Event
- If ALT decreases from ALT $\geq 5\times\text{ULN}$ and $<8\times\text{ULN}$ to $\geq 3\times\text{ULN}$ but $<5\times\text{ULN}$ (without elevated CPK, and/or myoglobin) and **GGT is $\geq 1.5\times\text{ULN}$** to $< 3\times\text{ULN}$, continue to monitor liver chemistries weekly.

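### Two sections conflict on when CPK and myoglobin are drawn. On the sparser schedule ten infusion visits lack both, and the weekly liver recheck panel omits both on either schedule, although most liver criteria cite them.

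*Combined protocol and SAP*

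**What the plan says.** **Visit schedule.** In Study Design, part a (Study Procedures and Schedule), CPK and myoglobin belong to the comprehensive evaluation only, which "will be conducted at weeks 0, 8, 16, 24, 32, 39-40, 52, 64". The other visits are described thus: "A less comprehensive set of evaluations (vital signs, AEs, CBC and metabolic panel, GGT, pregnancy test) will be conducted at weeks 2, 4, 12", and the list goes on with weeks 20, 28, 36, 40, 44, 48, 56 and 60. Appendix A confirms that the metabolic panel contains ALT.

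**Assessments section.** Study Procedures & Assessments lists the laboratory tests and ends: "CPK, myoglobin and urinalysis will be collected at every study visit and follow up week 64".

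**Liver rules.** Appendix C explains that its criteria were adapted because muscle injury itself raises ALT and AST in myositis. It does this by attaching the condition "without elevated CPK, and/or myoglobin" to most criteria. SAE items g, h and i under Safety Considerations and Adverse Events carry the same condition.

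**Weekly recheck.** For a subject in an increased-monitoring band who continues treatment, Appendix C says: "Subject must return weekly for repeat liver chemistries (ALT, AST, GGT, alkaline phosphatase, bilirubin) until they resolve, stabilize or return to within baseline". Neither CPK nor myoglobin is in that list.

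**The concern.** In this population a raised ALT is expected from the disease, so the muscle markers decide whether it counts as a liver signal. A criterion that cites a marker needs a marker value, and two parts of the plan do not supply one at the time the criterion would be applied.

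Take a subject at week 12 with ALT 9xULN, GGT 2xULN, and normal bilirubin and INR. If CPK and myoglobin are normal, the first ALT-absolute stopping criterion is met and Appendix C requires immediate discontinuation. If both are raised, that criterion is not met. The second ALT-absolute criterion needs GGT of at least 3xULN, and every ALT monitoring band ends below 8xULN, so no ALT-band rule applies. (HBV DNA testing for subjects with prior IVIG is a separate trigger.) The result turns on a test that one schedule does not list for week 12.

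Sites that follow different sections could handle and classify identical laboratory pictures differently. Safety is a stated study objective.

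**Working it through.** The plan states no figure for marker coverage, so there is none to reproduce. The check is a count.

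**1. Infusion visits** (Study Procedures and Schedule)
- Randomized phase: every four weeks from week 0 to week 36 is 10 infusions. The week 2 dose ("In addition, there will be a “loading dose” at week 2") makes 11.
- Open-label phase: every four weeks from week 40 to week 64 is 7.
- Total: 11 + 7 = 18. The Blinding section calls the open-label phase 20 weeks, which would end at 40 + 20 = week 60. If week 64 is not an infusion, the total is 17.

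**2. Infusion visits with CPK and myoglobin on the sparser schedule**

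| Assumption | 18 infusions | 17 infusions |
|---|---|---|
| The week 39-40 evaluation serves the week 40 infusion | 8/18 = 44.4% | 7/17 = 41.2% |
| It does not | 7/18 = 38.9% | 6/17 = 35.3% |

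The infusion visits without either marker are weeks 2, 4, 12, 20, 28, 36, 44, 48, 56 and 60: 18 - 8 = 10, or 17 - 7 = 10. Week 40 is an eleventh if the second row applies. If the every-visit statement governs, coverage is 18 of 18.

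**3. Age of the last scheduled marker value**, with the comprehensive visit placed at week 40
- Week 2: 2 - 0 = 2 weeks.
- Weeks 4, 12, 20, 28, 36, 44 and 56: 4 weeks each (for example 12 - 8).
- Week 48: 48 - 40 = 8 weeks. Week 60: 60 - 52 = 8 weeks.

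So 8 of the 10 visits have a value at most 4 weeks old, and 2 have a value 8 weeks old. If the evaluation falls at week 39, the ages at weeks 44 and 48 become 5 and 9 weeks.

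**4. Criteria that carry the marker condition**

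| Set | With condition | Total |
|---|---|---|
| Stopping: ALT absolute 1 of 2, ALT increase 2 of 2, bilirubin 0 of 1, INR 0 of 1, cannot monitor 2 of 2, symptomatic 1 of 1 | 6 | 9 |
| Increased monitoring: the 4 ALT bands, not the HBV DNA item | 4 | 5 |
| Liver SAE items g, h, i | 3 | 3 |
| All | 13 | 17 (76%) |

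The three unqualified stopping criteria are ALT at least 8xULN with GGT at least 3xULN, the bilirubin criterion and the INR criterion.

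**5. What the weekly recheck feeds**
- The two ALT-increase stopping criteria require a qualified ALT elevation with GGT of at least 3xULN to persist for 2 or 4 weeks.
- The step-down to twice-monthly monitoring after 4 weeks requires ALT below 3xULN, again with the marker condition.
- The recheck list supplies ALT, AST, GGT, alkaline phosphatase and bilirubin: the liver part of each test but not the muscle part.

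**6. Wording of the condition.** No time window is attached to the marker value. With one marker raised and the other normal, "without elevated CPK, and/or myoglobin" can be read as met or as not met.

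**The case against.** The strongest reply is that the gap may be narrower than the count suggests. The schedule text defers to Appendix A for detail, and that table may settle the visit schedule. It cannot be read by week in the available text. Its CPK and myoglobin rows carry fewer marks than the CBC row, and the ten visits listed above are exactly its asterisked weeks. That is a hint, not proof, and it sits against the every-visit statement. The table's note also provides for routine standard-of-care blood tests at infusion visits, and nothing forbids an unscheduled CPK. This stands: a careful site can obtain the value, but the plan does not tell it to.

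A reader might infer that the rules demand a same-day marker and cannot be applied whenever ALT rises. The documents do not support this. Appendix C states no window, so a value from an earlier visit is not excluded. Three stopping criteria need no marker, and even the sparser schedule covers 7 to 8 of 18 infusions.

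A reader might also extend the panel gap to the repeat tests due within 24 or 24-72 hours. Those follow a stopping event, after treatment has been discontinued, and are paired with follow-up assessments that include CPK, though not myoglobin. They do not feed the persistence criteria. The panel gap that matters is the weekly one.

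Finally, a reader might infer biased safety comparisons between arms. Randomization is generated for each site, so differing site practice does not by itself unbalance the arms, and the AE report is described as descriptive.

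**Conclusion.** The point holds as an unresolved contradiction that feeds safety rules. Two sections disagree on when CPK and myoglobin are drawn. On the sparser one, ten infusion visits have ALT and GGT without either marker, and coverage stays below half under every counting assumption (35% to 44%). The last scheduled value is usually at most 4 weeks old, but 8 weeks old at weeks 48 and 60.

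The weekly recheck omits both markers as written, and adopting the every-visit schedule does not add them to that list. At those visits and rechecks, the 13 of 17 criteria with the marker condition cannot be judged from the tests the plan lists.

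The visit count assumes that the schedule text is followed literally. The recheck finding assumes that the listed panel is complete. Neither depends on sample size or on any assumed event rate, and the documents do not allow an estimate of how many subjects would be affected.

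**What to change.** - Reconcile Study Procedures and Schedule, Study Procedures & Assessments and Appendix A to one laboratory schedule for CPK and myoglobin.
- Reconcile the weekly recheck panel with the stopping, increased-monitoring and step-down criteria in Appendix C, so that the markers those criteria cite are available when they are applied.
- State how old a marker value may be when a criterion is judged, and what and/or means when only one marker is raised.
- State whether week 64 is an infusion visit, so that the schedule has a fixed number of infusions.

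The cost is protocol wording and, if the reconciliation adds draws, two inexpensive assays on blood already being taken. The thresholds, the actions and the choice of clinical rule stay with the clinical team.
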